**Figure 12: workflow of the ADVANCE Codemapper**

The workflow of CodeMapper has three phases as shown in figure 6 which comprise multiple components. It starts from the case definition forms that are copied in the Codemapper. The Codemapper calls the Peregrine text indexing engine to identify medical concepts in the case definition. These are highlighted in the copied text. Concepts that belong to the semantic group of disorders in UMLS are pre-selected. After this automated selection the user can walk up and down the ontology to select further specify individually which concepts should be additionally included/excluded for further processing. Second, these concepts are related to concepts of the Unified Medical Language System (UMLS). The UMLS is then used to automatically retrieve codes that correspond to the selected UMLS concepts in a set of user defined coding systems. The concepts are displayed in a table alongside the associated codes in each coding system. Third, the user can revise codes of the mapping by applying concept-level operations. The user can add concepts, remove concepts, and retrieve more general or more specific concepts according to the hierarchical information in the UMLS. The set of targeted coding systems can be changed on-the-fly. After every operation, the code sets associated with the concepts are automatically updated. Feedback about the mapping is captured in comments that can be attached to the concepts.

Every operation is recorded in a history for later traceability. When saving her or his work, the user has a machine generated to summary of the modifications. The summary is added to the history. The mapping, comprised of the concepts and code sets is stored online together with the case definition, the initial mapping and history. All data can be downloaded as an Excel document to support incorporation into extraction scripts.

Availability: The CodeMapper application is freely available for non-commercial projects at <https://euadr.erasmusmc.nl/CoMap>.

The screenshot shows the CodeMapper application interface. At the top, there is a navigation bar with 'ADVANCE: pertussis PLAIN' and the 'ADVANCE CODE MAPPER' logo. Below the navigation bar, there are tabs for 'Case definition', 'Mapping', and 'History'. The main area is divided into several sections: 'Filter 8 available concepts', 'Modify 0 selected concepts', 'Search and add new concept', and 'Mapping'. The 'Mapping' section contains a table with columns for 'Name', 'Origin', 'ICD10CM', 'ICD9CM', 'ICPC', 'ICPC2EENG', 'ICPC2P', 'MDR', 'MSH', 'RCD', and 'RCD2'. The table lists various medical concepts related to pertussis, such as 'Pertussis', 'Bordetella infections', and 'Whooping cough due to unspecified organism', along with their corresponding codes in different coding systems.

Name	Origin	ICD10CM	ICD9CM	ICPC	ICPC2EENG	ICPC2P	MDR	MSH	RCD	RCD2
Pertussis	Pertussis	Whooping cough due to Bordetella pertussis	Whooping cough due to Bordetella pertussis [B pertussis]			Pertussis	Pertussis	Bordetella pertussis Infection, Respiratory	Pertussis	Pertussis
Bordetella infections	^ Pertussis						Bordetella infections	BORDETELLA INFECT	Bordetella infection	Bordetella infection
Infection due to Bordetella parapertussis (disorder)	^ Pertussis	Whooping cough due to Bordetella parapertussis	Whooping cough due to Bordetella parapertussis [B parapertussis]				Whooping cough due to Bordetella parapertussis [B parapertussis]			
Whooping cough due to unspecified organism	^ Pertussis	Whooping cough	Whooping cough	Whooping cough	Whooping cough	Whooping cough	Whooping cough		Whooping cough NOS	Whooping cough NOS

Figure 13: Screen-shot of the CodeMapper application

## Extraction of outcomes

The Codemapper lists will be sent to the databases who will be requested to extract the events and transform them in the common data model format. Codemapper will provide only disease codes, thus database experience should be used to define alternative algorithms. (e.g. using drugs as proxy, or using a combination of codes and drugs).

The case definition comprises information on the drugs and procedures that are used for the event. The event teams will collate the experience from the databases, the codes and drugs/procedures in the case definitions to suggest recommended 'component' algorithms is created (combination of disease codes,

---

text, procedures/measurements and drugs), and each database is invited to extract as many components as apply.

Local database contacts provide feedback on component algorithms and/or propose new ones. The final list of components results from an iterative process of refinement involving local experts and the data derivation leader.

Databases are making available different component algorithms per event.

Database experts extract the component algorithms and run the Algorithm Comparison Module of Jerboa. The result is a dataset of aggregated data which must be uploaded on the Remote Research Environment.

Extraction of codes for the POC have a time priority over the WP 4 events

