**Table 4: Characteristics of the Databases of ADVANCE Partners**

Datasource Country_name	Coverage, Region	Type of data	Years covered	Size (N persons)	Outpatient diagnoses	Inpatient diagnoses	Vaccines general	Prescribed/ dispensed drugs
BE_network of sentinel GPs	National	Surveillance network (paper based)	Since 1979	Based on patient contacts	Some (surveillance of specific diseases)	Specific diseases	No	No
BE_Pedisurv	National	Pediatric surveillance network of specific rare disease	Since 2002	National case based	Specific diseases	Specific diseases	no	No
DK_SSI	National	Record linkage	1996 - 2014	7.5 million	Yes (ICD-10)	Yes (ICD-10)	yes	yes
DK-AUH	Regional (Aarhus)	Record linkage	2004 - 2013	1.7 million	Yes (ICD-10)	Yes (ICD-10)	partial	yes
ES_BIFAP	National	GP	2002 - 2013	4.8 million	Yes (ICPC+free text)	yes (as text)	No (only influenza)	yes
ES_FISABIO	Regional (Valencia)	Record linkage	Since 2005	5 million	Yes (ICD-9)	Yes (ICD)	yes	yes
ES_IDIAP	Regional (Cataluña)	GP	Since 2005	5.8 million	Yes (ICD-9)	Yes	yes	yes
FI_HPVCCHRT	Trial participants	HPV RCTs+ extension through record linkage	Prospective since 2007	Around 20,000	Yes (ICD-10)	Yes (ICD-10)	yes	yes
IT_ARS	Regional (Tuscany)	Record linkage			no	Yes (ICD-9)	Not yet	yes
IT_ASLCR	Regional (Cremona)	Record linkage	2002 - 2013	454,188	No	Yes (ICD9)	Yes	yes
IT_Arianna	Regional (Casserta)	GP + record linkage	Since 2000	1.1 million	ICD9	ICD9	Not yet	yes
IT_PEDIANET	Regional (Veneto)	Family pediatricians	2004 - 2014	77,021	Yes	Yes	yes	yes
NL_IPCI	National	GP linked to RIVM vaccine registries	1996 - 2014	1.8 million	Yes (ICPC)	Yes (from letters/specialist)	no	yes
NL_RIVM	National	Case surveillance of infectious disease	?	16 million base population	Some (surveillance of specific diseases)	Specific diseases	no	No
SE_KI	National	Record linkage	1998 - 2010	9.4 million	Yes (ICD-10)	Yes (ICD-10)	partial	yes
UK_RCGP	National	GP	2003 - 2014	2.0 million	Yes (READ)	Yes (READ)	yes	yes

---

---

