### 7.2.7.2. Outcomes, Operationalization and Validation

#### OUTCOMES

The safety outcomes of interest are known reactions:

- Injection site reactions: erythema, edema, induration/ nodule/sterile abscess, pain/tenderness
- Fever
- Somnolence

- 
- Persistent crying, irritability
  - Generalized convulsions
  - HHE
  - Extensive limb swelling

A definition for somnolence is provided in Appendix 3. The Brighton Collaboration has case definitions available for injection site reaction [18], fever [19], persistent crying [20], generalized convulsions [21], HHE [22], and swelling (i.e. swelling at or near injection site as an increase in size or volume at the injection site that may extend to the entire limb according to severity) [23].

Events will be extracted from the electronic health care databases as diagnosis codes or text or by means of proxies. Mapping to ICD-9/10, READ and ICPC codes will be done semi-automatically using the ADVANCE code mapper. Algorithms for identification will be created with the databases and benchmarked against external sources and within consortium as described in section 7.1.

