### **VALIDATION**

Verification of the extracted codes and proxies for extraction of events will be done as part of the quality assessment and harmonization process (fingerprinting) prior to the start of the POC feasibility study. The verification will be done by comparing age-specific incidence rates between databases and comparison against external sources such as literature or other publicly available data. If possible, positive predictive values and sensitivity from prior studies will be retrieved. No chart validation at the patient level is foreseen for this POC feasibility study.

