  - The current methodology will not account for differences in vaccination schedules: different countries use different vaccines and schedules that may have changed over time. ATC codes will be used to identify which types of vaccines were used; this will allow stratification on vaccine types. Further, risks on schedule level will not be evaluated but will be evaluated on a dose level as each case is followed after each dose given.
  - Misclassification or missing information on vaccinations and events is a common limitation of observational studies conducted in electronic healthcare databases. Missingness and misclassification will be carefully followed and attempts will be made to implement data cleaning procedures (e.g. probability of wP or aP vaccine given the time of administration, dose according to timing in vaccination schedule, etc). Records with missing dates (i.e. birthdates, data of vaccination, date of event occurring) will be excluded. ATC code is a mandatory data field. A missing dose information will be derived (i.e., dose will be per recommendation, as determined by the database custodian based on knowledge of the local immunization schedule and as documented in an analytic variable generated for the purpose of the study).
  - aP and wP vaccine administration could have been overlapping. The period of potential overlap in a database will be excluded if aP or wP vaccine type information is missing (i.e. database entry is only referring to 'pertussis vaccine' and aP or wP is not specified).
  - The smallest possible time unit in electronic healthcare databases is 'days'. This could potentially make it difficult to judge whether vaccination happened before the event or vice versa when recorded on the same day. In this study, it is assumed a priori that vaccination occurs before the event whenever they are recorded on the same day, so the vaccination day is classified as risk period and starting at Day 0.

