**Figure 10: Example of population fingerprint output**

## Event fingerprinting

[figure not shown]
The overall aim of the event fingerprinting workflow (or also called data derivation workflow) is to obtain for each data source the best algorithm to extract an event/condition, and document this in a structured fashion. The full data extraction algorithm is a logical combination (AND, OR, or AND NOT) of components that could contain for example the following information:

- a diagnosis, recorded in a primary, secondary, inpatient care or other settings
- diagnostic evidence, for example laboratory measurements
- utilization of healthcare services specifically indicated to diagnose or treat that condition, such as a drug, a diagnostic test, a procedure or other health service

---

For instance, for some data sources a diagnostic code could be available for pertussis. In other data sources, results from blood tests may be available or surveillance data. In Figure 5 a high level graphical representation of the workflow is presented. In short the following questions are answered in each of the steps:

- Definition: How do we define the specific condition and its context?
- Collect experience: collection of how these conditions have been collected in the past. How can we leverage the valuable domain knowledge of the data custodians?
- Literature Search: what is the incidence/prevalence of this conditions in the countries of interest, this information will serve as an external benchmark to see whether the data retrieved have external validity
- Terminology Mapping: How can we translate the case definition into different terminology systems?
- Component algorithms: collection of information on how each database extracts the data which algorithms are used? Which is the list of unique component algorithms that each database should be invited to extract?
- Results Analysis: comparison of incidence rates between databases and with literature, and if possible component analysis, what is the influence of certain components on the incidence/prevalence?
- Final Decision: what is the best algorithm for each database, and archive this?

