## Results analysis

For all events the following statistics will be calculated

- 1) age specific incidence rates and standardized incidence rates. These data will be compared
  - a. Across databases
  - b. Against the literature
- 2) Overview of code counts (e.g. ICD 9 codes, READ codes)

Data needs to be submitted to RRE by the databases and the data will be post-processed and produce graphics that can be used for discussion.

All the information will be uploaded to the ADVANCE sharepoint

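### Drug-only event algorithms are allowed with no rule for drugs issued at the vaccination visit, so such records can count as risk-window events, and no planned check is split by window

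*Protocol*

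**What the plan says.** Section 7.2.7.2 (Outcomes) sets the general rule: "Events will be extracted from the electronic health care databases as diagnosis codes or text or by means of proxies". Appendix 1 (Extraction of outcomes) adds that the code mapper supplies disease codes only, "thus database experience should be used to define alternative algorithms. (e.g. using drugs as proxy, or using a combination of codes and drugs"). Drugs alone and drugs combined with codes are offered as separate options.

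Appendix 1 (Event fingerprinting) gives the one limit on a drug component. It describes such a component as "utilization of healthcare services specifically indicated to diagnose or treat that condition, such as a drug, a diagnostic test, a procedure or other health service".

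On timing, section 7.2.9 states that "it is assumed a priori that vaccination occurs before the event whenever they are recorded on the same day", and the vaccination day is day 0 of the risk period. Section 7.2.7.1 sets the fever window at 0-72 hours. In section 7.2.5 the SCCS baseline is days -31 to -8 and the days after the risk window up to day 31.

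On checking, section 7.2.7.2 (Validation) says "The verification will be done by comparing age-specific incidence rates between databases and comparison against external sources such as literature or other publicly available data" and "No chart validation at the patient level is foreseen for this POC feasibility study". Appendix 1 (Results analysis) repeats the check with "age specific incidence rates and standardized incidence rates. These data will be compared" across databases and against the literature. Appendix 1 (Component analysis) and Table 5 add comparison of component algorithms and estimates of sensitivity and PPV; Table 5 also lists specificity. None of these is described as split by risk and baseline window.

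**The concern.** For several outcomes here a drug record is not independent of the exposure. A drug issued at the vaccination visit, before any event or without one, carries the date of the dose. Under the day-0 rule a drug-only algorithm turns it into an event inside the risk window. This is false-positive outcome classification timed by the vaccine.

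The SCCS does not remove it. Its baseline excludes day 0, so such records enter only the risk period, and self-matching controls for fixed characteristics of the child, not for false events tied to the dose.

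The results travel. Risk-window rates fill the effects table for the benefit-risk model (section 7.3.1, Table 6). The wP ratio from the SCCS is multiplied onto baseline rates in databases that lack wP data (section 7.2.1 and the Abstract), so an artefact in one database can reach others.

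**Working it through.** The protocol gives no figure on this point, so nothing of its own can be reproduced. The calculations below show direction and size.

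**1. Effect on the wP-aP contrast**

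Inputs from section 5 (Safety Studies): fever of at least 37.8 °C after dose 1, 27.3% with wP and 4.2% with aP, a ratio of 27.3/4.2 = 6.5 and a difference of 23.1 points. Assumed: a share q of visits with a drug record unrelated to fever, equal for both vaccines.

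Observed risk = f + (1 - f)q, where f is the true risk. At q = 10%: wP 0.273 + 0.727 × 0.10 = 34.6%; aP 0.042 + 0.958 × 0.10 = 13.8%.

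| q | wP | aP | Ratio | Difference (points) |
|---|---|---|---|---|
| 0 | 27.3% | 4.2% | 6.5 | 23.1 |
| 1% | 28.0% | 5.2% | 5.4 | 22.9 |
| 5% | 30.9% | 9.0% | 3.4 | 22.0 |
| 10% | 34.6% | 13.8% | 2.5 | 20.8 |
| 20% | 41.8% | 23.4% | 1.8 | 18.5 |

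The difference shrinks only by the factor (1 - q). Rarer outcomes are hit harder on the ratio scale. For very high fever after dose 4 (0.8% wP, 0.2% aP, ratio 4.0), q = 1% gives 1.79%/1.20% = 1.5.

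The result also depends on how much true fever reaches the record. If only 10% of the 27.3% and 4.2% were recorded (assumed), q = 1% gives 3.70%/1.42% = 2.6 instead of 5.4.

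**2. Unequal prescribing**

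- 20% with wP and 10% with aP: 41.8%/13.8% = 3.0, but the difference grows from 23.1 to 28.1 points.
- 30% with wP and 2% with aP: 49.1%/6.1% = 8.0, so the ratio also widens.

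**3. Ratio with no vaccine effect**

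Assumed: 0.5 background events per child-year, a 4-day window (days 0-3) and q = 1%. Expected events per window = 0.5 × 4/365.25 = 0.0055. Ratio = (0.0055 + 0.01)/0.0055 = 2.8. With background rates of 0.2 to 1.0 per child-year it runs from 5.6 down to 1.9.

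**4. What the planned checks would show**

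Under the assumptions of step 3, ignoring vaccine-caused fever:

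- Six years pooled, 4 doses: 0.04/(0.5 × 6) = 1.3% higher.
- First year from 1 month of age, 3 doses: 0.03/(0.5 × 11/12) = 6.5% higher.
- One month of age containing a dose: 0.01/(0.5/12) = 24% higher.

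If all background records were true events, overall PPV would be 3.0/3.04 = 99%. In-window PPV over 4 doses would be 0.0219/(0.0219 + 0.04) = 35%. An overall PPV can therefore look sound while validity in the window is poor.

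**The case against.** The strongest reply is that nothing is fixed yet. Appendix 1 describes candidate components, given as examples. They are then compared, a proposal is made per database, and the chosen algorithm is stored with a written reason. Drug components are meant to be specific to the condition, and antipyretics are never named. This stands in part: a reader might infer that some database will use a drug-only fever algorithm, and the documents do not show that. Table 4 lists the database marked "Regional (Cremona") with vaccines and drugs but no outpatient diagnoses, yet it is only a candidate and may simply not supply fever. The specificity wording, however, does not shut out an antipyretic for fever, and it says nothing about when the drug was issued.

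A reader might also infer that the rate checks would hardly move. That fits only a rate pooled over about six years. The checks are age-specific, and infant bands would shift; the band width is not stated. But section 7.2.9 already expects rates to differ by database type, so a shift would not point to visit prescribing.

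A third tempting inference is that the wP-aP contrast must shrink. That needs similar prescribing for both vaccines and is marked only on the ratio scale.

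Finally, section 7.2.9 concedes that the estimates may not be the true ones, and drugs issued before the vaccination day do not enter the risk window. Both are right. The second narrows the problem to records from day 0 onward, which is why a ban on all drug-only components would go further than the problem shown.

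**Conclusion.** The point holds as a conditional one. The protocol allows drug-only identification of events, has no rule for drugs issued at the visit, and counts same-day records as following vaccination. Where a database takes that option for a mild outcome, the risk-window rate and the SCCS ratio are biased upward for any visit prescribing without an event.

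The direction of the wP-aP error depends on whether such prescribing differs between the vaccines. With equal prescribing and the protocol's own dose-1 fever figures, the ratio of 6.5 falls to 5.4 at 1% and to 2.5 at 10%. The prescribing share, background rate and recording share are all assumptions; the protocol gives none of them. The planned checks may register a shift in infant age bands but cannot attribute it, because none compares the risk window with baseline.

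**What to change.** In Appendix 1, for fever, injection-site pain, crying/irritability and somnolence, state that a drug-only record dated on the vaccination day is not counted as an event unless a diagnosis code or text for the same event accompanies it.

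In the component analysis, before the final algorithm is chosen:

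- tabulate each component's counts by day -7 to +7 around doses, which would also expose any excess on the days just after the visit that the day-0 rule does not reach;
- report code- or text-only rates beside drug-based rates, inside and outside the risk window.

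The cost is one sentence and one extra set of tables from data already extracted. The downside is somewhat lower sensitivity for mild outcomes in databases with few outpatient diagnoses.

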## Results analysis

For all events the following statistics will be calculated

- 1) age specific incidence rates and standardized incidence rates. These data will be compared
  - a. Across databases
  - b. Against the literature
- 2) Overview of code counts (e.g. ICD 9 codes, READ codes)

Data needs to be submitted to RRE by the databases and the data will be post-processed and produce graphics that can be used for discussion.

All the information will be uploaded to the ADVANCE sharepoint

### *Component analysis*

Different algorithms using specific components will be compared and analyzed. Conclusive decision will be taken on algorithms to be used for final extractions

Using the Analysis Tool developed within the EMIF project, local experts are allowed to test the extracted component algorithms in different logical combinations using Boolean operators (AND, OR, AND NOT) in order to build more complex extraction strategies, referred to as *composite algorithms* (e.g.  $\geq 1$  primary care diagnosis AND  $\geq 1$  test result positive).

The event team leader makes a proposal for each database. Local experts choose the composite algorithm that they recommend for the identification of the event in their data source, following or challenging the recommendation of the event team leader. Each recommended composite algorithm is stored together with a comment of a data source expert explaining its choice.

An estimate of the sensitivity and PPV is also provided based on previous validation studies, local expert's expectations, information from other data sources and procedures developed in WP4.

## Archiving of final algorithms and fingerprint results

Each database will submit the final algorithm that was used both in code as well as in narrative (pseudo code). All this information will be stored in the Codemapper/Sharepoint.

## Vaccine fingerprinting

---

Initial discussions with the databases showed that most databases will have information on the vaccinetype and the ATC code or at least part of it. In the Anatomical Therapeutic Chemical (ATC) classification system, the active substances are divided into different groups according to the organ or system on which they act and their therapeutic, pharmacological and chemical properties. Vaccines are coded in different Anatomical groups although the majority are part of the therapeutic subgroup J07.

The divisions are made between bacterial (J07A), viral (J07B), bacterial & viral (J07C), other vaccines (J07D) and cancer vaccines (in L03). Bacterial vaccines are divided in 14 subgroups, viral vaccines are divided in 13 subgroups, grouping is based on the vaccine preventable disease. Within the groupings the most detailed level finishes with the type of antigen.

